#### 2. **Analytical approach**

Duration will be summarised for each AChE-I categories by treatment group.

AchE-I events with a start time less than or equal to 6 hours after the latest dose administered will also be flagged in the dataset.

#### 4.6.2.2. COVID-19 Assessment and COVID-19 AEs

A standardized MedDRA Query (SMQ) will be used to identify all COVID-19 AEs. COVID-19 assessments for participants with COVID-19 AEs will be summarized.

#### 4.6.2.3. Impact of COVID-19 Pandemic on Safety Results

The summary of the incident rates of AE before and after the start of the COVID-19 will not be produced since this study starts after the beginning of the COVID-19 pandemic.

#### 4.6.2.4. Quantitative Screening for Identification of Potential Adverse Reaction

Frequentist approach to screen for potential ARs will be used. Specifically, the Crowe method [Crowe, 2013] will be applied for initial screening of the large number of adverse events to generate a “short list” of potential ARs. Due to the smaller sample size than the global studies, this method is based on the HLT relative risk (incidence rate on gepotidacin arm divided by that on nitrofurantoin arm).

Screening criteria endorsed are displayed in [Table 3](#).

**Table 3 Criteria for Quantitative Screening for Potential ARs.**

Absolute Incidence in Nitrofurantoin Subjects	HLT relative risk (Gepotidacin vs Nitrofurantoin)	95% CI for HLT RR*
No condition	≥1.25	No condition

Note that any event which has not occurred on nitrofurantoin arm but occurred on gepotidacin arm will be included in the “short list”. In addition, the following AEs will automatically be included in the “short list” of potential ARs for further qualitative evaluation:

- QT Prolongation: It is a very rare serious event that has been observed in early phase gepotidacin studies and therefore needs further evaluation. It is identified using HLT “ECG investigations”.
- Serious and severe adverse events: The incidence of serious and severe AEs is expected to be very low and the qualitative assessment will be applied directly to these events without going through the quantitative screening process.
- Fungal infections: It is a known AR for nitrofurantoin. It is identified using HLT “Fungal infections NEC”.
- Hepatobiliary disorders: It is a known AR for nitrofurantoin. It is identified using HLT “Hepatic and hepatobiliary disorders”.
- AESI specified in Section [6.2.2.1](#).
- AEs with PT as “Hyperhidrosis” or “Dysarthria”

A summary table of treatment emergent adverse events meeting the pre-specified quantitative screening criteria by SOC, HLTs and PTs with incidence (%) for each treatment group, RR, and the associated 95% CI will be generated.

In addition, the following outputs will be generated.

- Summary of treatment emergent adverse events by SOC, HLT and PTs by subgroups (Consistency check between subgroups: Actual Age Category, and Renal Impairment Evaluated by Baseline CrCL)
  - Actual Age Category: <18, 18-64 and >=65
  - Renal Impairment (Baseline Creatinine Clearance): Normal (>=90mL/min), Mid-Impairment (>=60 to 89 mL/min), Moderate Impairment (>= 30 to 59 mL/min), Severe Impairment (< 30mL/min), Missing
- Incidence rate of treatment emergent AEs according to different attributes by HLT and treatment group (Consistency check in AE attribute: AEs related to study treatment, AEs leading to permanent discontinuation of study treatment, AE leading to dose reduction, AE leading to dose interruption /delay, SAEs related to study treatment, Fatal SAEs, and Fatal SAEs related to study treatment)
- Summary of treatment emergent AEs by HLT and Maximum Grade (Consistency check in AE attribute)
- Summary of Cumulative Incidence of Treatment Emergent Adverse Events (HLTs) by Time to First Occurrence (Temporal association). The categories of time to first occurrence are below.
  - <= 2 days, <= 3 days, <= 4 days, <= 5 days, <= 6 days, <= 7 days, <= 8 days, <= 9 days, >= 10 days

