	A substantial increase in Cmax and AUC and decrease in clearance was observed in volunteer participants with severe hepatic impairment.	
Renal Effects In preclinical trials, mild to moderate tubular degeneration was noted in the rat and proteinuria in the dog. Proteinuria was also observed in humans.	No clinical evidence of renal toxicity has been seen in clinical trials to date. A substantial increase in Cmax and AUC and decrease in clearance was observed in severe renal impairment/ESRD participants not on hemodialysis and in ESRD participants requiring hemodialysis (note: gepotidacin may have been administered at any time other than when receiving dialysis).	Participants with severe renal impairment/ESRD (including those who may require dialysis) are excluded from Phase III trials. See Section 5.2 for excluded medical conditions. Monitoring criteria have been implemented.
Reproductive System Effects Preclinical studies demonstrated that gepotidacin was not genotoxic and no drug related malformations were observed. Although positive in vitro findings for clastogenicity, consistent with a mechanism related to mammalian topoisomerase II inhibition were found, in vivo data from rat micronucleus and COMET assays suggest that gepotidacin does not pose a genotoxic hazard to humans. Gepotidacin effects on embryofetal development were limited to decreased fetal weights for male and female fetuses in rats and decreased fetal weights and increased fetal resorptions (fetal deaths) in mice, both at maternally toxic doses. These occurred at clinically relevant exposure (65 µg.h/mL in rat and 35µg.h/mL in mouse).	There are no data on the use of gepotidacin in pregnant women.	Gepotidacin is not recommended in pregnant or nursing mothers. Pregnancy testing requirements in this study minimize the risk of exposure to a fetus. See 10.4 for contraceptive measures and Section 8.2.5 for required pregnancy testing.
Other		
Nitrofurantoin	The most frequent AEs possibly or probably related to oral nitrofurantoin treatment are nausea (8%),	Close monitoring of clinical parameters and AEs (Section 1.3) will be conducted, and treatment

Potential Risk of Clinical Significance	Summary of Data/Rationale for Risk	Mitigation Strategy

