	
headache (6%), and flatulence (1.5%). As with gepotidacin, there is also a need to monitor for C. difficile-associated diarrhea during nitrofurantoin treatment.
 
Nitrofurantoin is contraindicated for patients with anuria, oliguria, or significant impairment of renal function; pregnant patients at term (38 to 42 weeks' gestation), during labor and delivery, or when the onset of labor is imminent; neonates under 1 month of age; and patients with a previous history of cholestatic jaundice/hepatic dysfunction associated with nitrofurantoin.
 
Rare adverse reactions that generally occur in patients receiving treatment for 6 months or longer are acute, subacute, or chronic pulmonary reactions, with potential insidious development of chronic pulmonary reactions (diffuse interstitial pneumonitis or pulmonary fibrosis, or both).
 
Peripheral neuropathy has occurred, which may be enhanced for patients with renal impairment, anemia, diabetes mellitus, electrolyte imbalance, vitamin B deficiency, and debilitating disease.
 
Nitrofurantoin has induced the occurrence of hemolytic anemia of the primaquine sensitivity type, which appear to be linked to a glucose-6-phosphate dehydrogenase deficiency in the red blood cells of the affected patients.
	
monitoring and evaluation criteria (Section 7.1.1) will be utilized to mitigate hepatic effects.
 
Because planned treatment in this study is only 5 days, the probability for adverse reactions associated with long-term use is low.
 
The exclusion criteria for this study include contraindications to nitrofurantoin use and exclude participants at risk for nitrofurantoin adverse reactions, including acute porphyria as an example of a rare genetic risk (see Section 5.2).
 
Participants with a history of sensitivity to nitrofurantoin, or components thereof, will not be allowed to enroll in the study (Section 5.2). Participant's medical history will be carefully evaluated for history of hypersensitivity.
 
Participants must agree not to use antacid preparations containing magnesium trisilicate or uricosuric drugs during study treatment (see Section 5.2).
 
Suspected C. difficile infection will be managed according to a prespecified algorithm provided in 10.7.
 
Precautions related to nitrofurantoin are summarized in detail in the Study Reference Manual.

Potential Risk of Clinical Significance	Summary of Data/Rationale for Risk	Mitigation Strategy

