### 5.1.3. Proposed Sample Size

Assuming a 36% evaluability rate, approximately 300 participants will be enrolled and randomized to either gepotidacin or nitrofurantoin in a 3:1 ratio to achieve 108 participants in the micro-ITT NTF-S population (i.e. approximately 81 participants on gepotidacin and 27 on nitrofurantoin). Enrolment will continue until the approximate target number of participants in the micro-ITT NTF-S Population has been reached. This study will be conducted at multiple sites in Japan.

**Note:** Enrolled means a participant's, or their legally acceptable representative's, agreement to participate in a clinical study following completion of the informed consent process. Potential participants who are screened for the purpose of determining eligibility for the study, but do not participate in the study, are not considered enrolled, unless otherwise specified by the protocol. A participant will be considered enrolled if the informed consent is not withdrawn prior to participating in any study activity after screening.

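### The adverse-reaction short list is screened against nitrofurantoin and automatically adds some known nitrofurantoin reactions, but not headache, so a headache reaction shared by both drugs could miss the planned qualitative evaluation

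*SAP*

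**What the plan says.** SAP 4.6.2.4 describes an initial screen that reduces the adverse events to a short list of potential adverse reactions. Because the trial is smaller than the global studies, "this method is based on the HLT relative risk (incidence rate on gepotidacin arm divided by that on nitrofurantoin arm". Table 3 sets the threshold at 1.25 or more, with no condition on the confidence interval or on the incidence under nitrofurantoin. A zero-cell rule adds that "any event which has not occurred on nitrofurantoin arm but occurred on gepotidacin arm will be included in the “short list".

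Some events go on the list whatever their ratio, for further qualitative evaluation:

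- QT prolongation.
- Serious and severe events, where "the qualitative assessment will be applied directly to these events without going through the quantitative screening process".
- Two groups justified only by the comparator: "Fungal infections: It is a known AR for nitrofurantoin" and "Hepatobiliary disorders: It is a known AR for nitrofurantoin".
- The adverse events of special interest in SAP 6.2.2.1.
- Hyperhidrosis and dysarthria.

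The nitrofurantoin entry in protocol 2.3.1 gives the most frequent possibly or probably related events as nausea (8%), headache (6%) and flatulence (1.5%). SAP 6.2.2.1 treats the whole gastrointestinal system organ class as of special interest, so nausea and flatulence are listed automatically. Headache is not on the automatic list and is not in the cardiovascular, gastrointestinal, *C. difficile* or acetylcholinesterase-inhibition definitions.

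**The concern.** The screen looks for reactions to gepotidacin, but its reference is an active drug with reactions of its own. It therefore asks whether an event is commoner than on nitrofurantoin. An event that both drugs cause at the same rate sits at a ratio of 1, below the threshold, and is listed only if chance pushes the observed ratio up.

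The two comparator-based bullets have the effect of a remedy for this. Among the three most frequent nitrofurantoin-related events in the protocol, that remedy and the special-interest rule together reach nausea and flatulence but not headache. Hepatic reactions, which the same protocol entry describes as rare, are covered. If gepotidacin also causes headache, the term may not reach the qualitative evaluation that the SAP sets up for shortlisted events.

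**Working it through.** **Inputs**

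- Arm sizes: "approximately 300 participants will be enrolled and randomized to either gepotidacin or nitrofurantoin in a 3:1 ratio" (SAP 5.1.3), so 300 × 3/4 = 225 and 300 × 1/4 = 75. The SAP states no operating characteristic for the screen, so there is no figure of its own to reproduce for it. Its sample-size arithmetic does reproduce: 300 × 0.36 = 108, split as 81 and 27.
- Headache on nitrofurantoin: 6% (protocol 2.3.1).
- Headache on gepotidacin: not given. **Assumed** equal to nitrofurantoin, with a range.
- Listing rule: SAP 4.6.2.4 and Table 3.

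**Rule in counts.** Let X be the number of participants with headache on gepotidacin and Y the number on nitrofurantoin. The ratio is (X/225)/(Y/75) = X/(3Y). The term is listed if X ≥ 3.75Y when Y > 0, or if X ≥ 1 when Y = 0. At 6% on both arms the expected counts are 13.5 and 4.5. With Y = 4 the rule needs X ≥ 15, and with Y = 5 it needs X ≥ 19 (3.75 × 5 = 18.75). Both exceed the 13.5 expected.

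**Probability.** With X ~ Bin(225, p) and Y ~ Bin(75, p) independent, P(listed) is the exact sum of P(X = x)P(Y = y) over all pairs that satisfy the rule.

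| Shared rate (225 vs 75) | Listed | Left off |
|---|---|---|
| 3% | 42.3% | 57.7% |
| 6% | 36.9% | 63.1% |
| 8% | 34.2% | 65.8% |
| 10% | 31.2% | 68.8% |

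**Sensitivity, with 6% on nitrofurantoin**

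- Arm sizes, 6% on both arms: left off 62.0% (180/60), 62.7% (210/70), 63.5% (240/80) and 65.0% (285/95). This matters because enrolment runs until the microbiological target is met and the Safety population excludes one site.
- Unequal rates (225/75): with gepotidacin at 4%, 5%, 7.5%, 8% or 10%, left off 83.0%, 73.8%, 47.0%, 42.0% or 25.2%.
- Form of the rule: a strict threshold above 1.25 gives 65.0%. Without the zero-cell rule it is 64.0%.
- Severe cases: suppose one severe gepotidacin headache were enough to list the term, which the SAP does not say. If 1%, 2% or 5% of headaches were severe, 63% would fall to 56%, 49% or 34%. SAP 4.6.2 imputes a missing grade as severe, which works in the same direction.

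**With headache listed automatically.** It would be missed only if no gepotidacin participant reported it. At 6% that probability is 0.94^225, about 9 in 10 million.

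**The case against.** The strongest reply is that nothing in the documents suggests that gepotidacin causes headache. The gepotidacin rows of protocol 2.3.1 do not mention it, and no rate is given. The 6% is nitrofurantoin's figure for related events of one kind, whereas the screen counts all treatment-emergent events by HLT. This stands: 63% is a scenario and not a forecast. The 3% to 10% range covers part of the mismatch in definition, but only if the two arms stay equal.

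Second, headache stays visible. SAP 4.6.2 tabulates all events, intervention-related events and common events (1% or more). At 6%, the chance that headache reaches 3 of 225 on gepotidacin, and so the 1% table, exceeds 99.9%. The further HLT outputs in SAP 4.6.2.4, on relatedness, grade and timing, also appear not to be limited to shortlisted terms. This stands too. A reader might infer that the safety conclusion would then reflect the choice of comparator. The documents do not support that: they call the step initial screening, and they do not say that an unlisted event is barred from causality assessment.

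Third, the SAP states no principle that every known nitrofurantoin reaction must be listed. That is an inference from two bullets, and fungal infection is not in the protocol's nitrofurantoin entry at all. Nor is headache the only reaction left out, as a reader might suppose. The protocol also names peripheral neuropathy, pulmonary reactions and hemolytic anemia, none of which is a named automatic item, although dyspnoea is an acetylcholinesterase-inhibition term. Headache is alone only among the three most frequent events.

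Finally, equal background headache would be listed just as often as an equal shared reaction, so leaving a nonspecific event to the ratio is partly a choice for specificity. That is fair, and it is the cost of the fix. It does not explain why the comparator-based bullets stop where they do.

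**Conclusion.** The point holds as a cheap improvement. The screen cannot readily pick up a reaction that both drugs share, and the SAP's automatic list does not reach headache, the second most frequent related event that the protocol gives for the comparator. If non-serious, non-severe headache were equally common on both arms at 3% to 10%, with 225 and 75 treated, it would be left off the short list about 58% to 69% of the time, and 63% at 6%. The figure is lower if gepotidacin's rate is the higher one, or if a single severe case lists the term. It is higher if gepotidacin's rate is below nitrofurantoin's.

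The effect is confined to missing the pre-specified qualitative evaluation. Headache data are not removed from safety reporting, and the primary and secondary efficacy results are untouched.

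**What to change.** In SAP 4.6.2.4, add one bullet to the automatic-inclusion list for the HLT that contains the preferred term Headache. Give as the reason that it is a known nitrofurantoin reaction under protocol 2.3.1, in the same form as the fungal and hepatobiliary bullets. No new data or analyses are needed. The cost is one SAP line and one more HLT in the qualitative evaluation, which will be reviewed even if headache proves to be background only.

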#### **4.6.2.5. Impact of GCP violation**

This analysis is based on Safety-ALL population. For transparency, the number and percentage of participants experiencing any adverse events will be presented by treatment arm, SOC and PT.

### **4.6.3. Additional Safety Assessments**

#### **4.6.3.1. Laboratory Data**

Summaries of worst-case grade increase from baseline grade will be provided for all the lab tests that are gradable by DMID criteria (Section 6.2.4). These summaries will display the number and percentage of subjects with a maximum post-baseline grade increasing from their baseline grade. Any increase in grade from baseline will be summarized along with any increase to a maximum grade of 3 and any increase to a maximum grade of 4. Missing baseline grade will be assumed as grade 0. For laboratory tests that are graded for both low and high values, summaries will be done separately and labelled by direction, e.g., sodium will be summarized as hyponatremia and hypernatremia separately. The determination of worst case post-baseline takes into account both planned and unscheduled assessments.

For lab tests that are not gradable by DMID criteria (Section 6.2.4), summaries of worst-case changes from baseline with respect to normal range will be generated. Decreases to low, changes to normal or no changes from baseline, and increases to high will be summarized for the worst-case post-baseline. If a subject has a decrease to low and an increase to high during the same time interval, then the subject is counted in both the “Decrease to Low” categories and the “Increase to High” categories.

Separate summary tables for change from baseline in haematology, and chemistry laboratory tests will be produced. Liver function laboratory tests will be included with chemistry lab tests.

A summary of Liver Monitoring/Stopping Event Reporting will be summarized. For participants with more than one liver stopping or liver monitoring event, only data related to the earliest most severe criteria event is included in the summary.

Abnormal liver chemistry results will be summarized by increasing folds above the upper limit of normal (ULN) including tests of interest and thresholds as follows (including data at all the visit including unscheduled visits):

- ALT or AST > 3xULN and Total Bilirubin > 2xULN\*
- ALT or AST > 3xULN and ALP < 2xULN and Total Bilirubin  $\geq$  2xULN
- ALT or AST > 3xULN and Total Bilirubin > 1.5xULN
- Hepatocellular injury:  $(ALT/ALT\ ULN)/(ALP/ALP\ ULN) \geq 5$  and ALT  $\geq$  3xULN \*\*
- ALT or AST  $\geq$  20xULN
- ALT or AST  $\geq$  10xULN
- ALT or AST  $\geq$  8xULN
- ALT or AST  $\geq$  5xULN
- ALT or AST  $\geq$  3xULN
- ALT  $\geq$  20xULN
- ALT  $\geq$  10xULN
- ALT  $\geq$  8xULN
- ALT  $\geq$  5xULN
- ALT  $\geq$  3xULN
- AST  $\geq$  20xULN
- AST  $\geq$  10xULN
- AST  $\geq$  8xULN
- AST  $\geq$  5xULN
- AST  $\geq$  3xULN

- Total Bilirubin > 2xULN
- Total Bilirubin > 1.5xULN
- Total Bilirubin > 2xULN and a portion of Direct Bilirubin  $\geq 35\%$  on the same day
- Total Bilirubin > 1.5xULN and a portion of Direct Bilirubin  $\geq 35\%$  on the same day

\*: The total Bilirubin elevation must occur on or up to 28 days after the ALT elevation

\*\*: sign of hepatocellular injury, ALT and ALP values must occur on the same day.

Urinalysis results will be summarized using descriptive statistics. The severity of renal impairment will be evaluated and summarized according to the method in Section [6.2.2.2](#).

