9.3.4. Safety Analysis

All safety analyses will be performed on the Safety Population. All reported AEs will be coded using MedDRA and summarized by system organ class and preferred terms.

The safety estimand will use a treatment policy strategy for the ICE of study treatment discontinuation, as safety will be assessed at all post-baseline assessments irrespective of whether the participant completed the treatment.

Treatment-emergent AE (TEAE) is defined if AE onset date/time is on or after treatment start date/time. The number and proportion of treatment-emergent AEs, study treatment-related AEs, deaths, SAEs, and AEs leading to study treatment or study withdrawal will be provided. Treatment-emergent AEs will be summarized by maximum intensity.

Adverse events of special interest will include CV, gastrointestinal, and *Clostridiooides difficile infection or colitis* events. In addition, AEs associated with acetylcholinesterase inhibition are also considered special interest. As described in the SAP, manual and programmatic reviews of AEs/preferred terms will be used to assess these events.

The severity of specified AEs and laboratory abnormalities will be graded according to the modified DMID toxicity grading system (Section 10.12). Data will be tabulated and reported by absolute grade for Grades 3 and higher, and shift tables, as appropriate.

Change from baseline over time in laboratory parameters, ECGs and vital signs will be summarized with descriptive statistics. The frequency of laboratory abnormality events along with the shift from baseline to the worst-case post-baseline value will be provided. Abnormal liver chemistry results will be determined using increases above the upper limit of normal.

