#### **4.6.3.2. Vital Signs**

The number of participants with worst case vital sign results relative to potential clinical importance (PCI) criteria which are post-baseline relative to baseline will be summarised by test and category. The summary will include baseline data and worst case post-baseline, and planned visit. The baseline categories are: Low, within Range and High for PCI criteria. The change categories for PCI criteria are: To Low, To within Range or No Change, To High. The determination of worst case post-baseline takes into account both planned and unscheduled assessments. Changes in value from baseline for each vital sign will be summarized at every assessed time point. All vital sign data will be listed.

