#### **4.9. Changes to Protocol Defined Analyses**

There were changes below to the originally planned statistical analysis specified in the protocol amendment 2 (Dated: [07-NOV-2022]).

- Added the analysis populations due to GCP violation
- Amended the micro-ITT NTF-S (Global) population to align with the primary analysis population (i.e., IA set) in the global studies (204989 and 212390).
- Originally, missing data in this study was to be imputed for tipping point analysis and multiple imputation sensitivity analysis for missing data. However, a conservative approach will be taken in this study where all missing data (regardless of the reason for missingness) will be imputed as therapeutic failure. Note that the missing data in the global studies (204989 and 212390) will be imputed for tipping point analysis and multiple imputation sensitivity analysis.

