## 6.2.7. Assessment Window

Unscheduled and withdrawal visit data will be slotted into a target visit based on visit window defined in the table below. If there are multiple assessments within the same window, the closest one to the target day will be taken in the slotting. If multiple records are equally close to the target day, then the later record will be utilized. For post-baseline records collected outside the analysis visit window, a blank analysis visit label will be assigned.

Analysis Set / Domain	Parameter (if applicable)	Target	Analysis Window		Analysis Timepoint
			Beginning Timepoint	Ending Timepoint	
All	All	Day 3	Day 2	Day 5	On-therapy
All	All	Day 12	Day 9	Day 16	Test-of-Cure
All	All	Day 28	Day 21	Day 31	Follow-up

The procedure of the analysis visit assignment is as follows.

1. Calculate the analysis days for planned visit, unscheduled visit, and early withdrawal visit with non-missing outcome if applicable. The calculation of the analysis days is provided in Section 6.2.6.
2. Slot the visits to each of analysis timepoint according to the above table.
  - a. If there are multiple assessments within the same windows, the closest one to the target day will be taken in the slotting.
  - b. If multiple records are equally close to the target day, then the later record will be utilized using the sequence number in SDTM dataset.
  - c. For post-baseline records collected outside the analysis visit window, a blank analysis visit label will be assigned. Such assessments will not be included in any of the by visit summaries. Descriptive summaries that are shown for “any assessment post baseline” e.g. maximum/minimum/ worst case post baseline, will use all assessments irrespective of whether they fall in an analysis visit window.

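### The liver-threshold table in SAP 4.6.3.1 draws on all visits, so as written it can count pre-dose bilirubin or AST values as study liver abnormalities

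*SAP*

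**What the plan says.** SAP 4.6.3.1 (Laboratory Data) lists threshold rows for ALT, AST and total bilirubin, alone and combined, and defines their data source in a bracket: "including data at all the visit including unscheduled visits". The rows are absolute multiples of the ULN.

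Three rows combine ALT or AST above 3xULN with bilirubin. Only the first carries a timing footnote: "The total Bilirubin elevation must occur on or up to 28 days after the ALT elevation". The second adds an ALP condition. The third reads "ALT or AST > 3xULN and Total Bilirubin > 1.5xULN". Neither of these two has a timing rule.

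The DMID-grade summary in the same section is restricted: "The determination of worst case post-baseline takes into account both planned and unscheduled assessments". The summary of tests that DMID does not grade is also limited to the worst post-baseline result. For vital signs, SAP 4.6.3.2 keeps the two periods apart: "The summary will include baseline data and worst case post-baseline, and planned visit". SAP 4.6.3.3 treats ECG in a similar way. Protocol 9.3.4 says that "safety will be assessed at all post-baseline assessments irrespective of whether the participant completed the treatment".

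**The concern.** A table of liver abnormalities in a drug study is read as what happened after dosing. If pre-dose results enter it, a participant who arrived with a raised bilirubin or AST appears in the same row as one whose value rose on treatment, and the table does not separate them.

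The two combined rows without a timing rule matter most. Concurrent enzyme and bilirubin elevation is the pattern a safety reader looks for. There, a row could be met by a bilirubin seen only before the first dose together with an enzyme rise seen only afterwards.

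**Working it through.** No figure in the plan needs reproducing. The check sets the texts side by side and then follows one illustrative participant through the rules.

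**Step 1. Is Baseline among all visits?** The Schedule of Activities (Protocol 1.3) places chemistry at Baseline pre-dose, On-therapy and TOC. Protocol Section 8 counts Baseline as one of the four planned visits. SAP 4.1.2 (baseline), 6.2.5 (study periods) and 6.2.7 (windows) do not take Baseline out of this table. It is therefore included on a literal reading.

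**Step 2. How do the comparable summaries define scope?**

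| Summary | Data used |
|---|---|
| DMID grade increase (SAP 4.6.3.1) | Post-baseline, planned and unscheduled |
| Tests not graded by DMID (SAP 4.6.3.1) | Worst case post-baseline |
| Vital signs, ECG (SAP 4.6.3.2, 4.6.3.3) | Worst case post-baseline, with baseline shown separately |
| Liver thresholds (SAP 4.6.3.1) | All visits |

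The wider scope is not needed to keep stray records. Under SAP 6.2.7, summaries labelled as any post-baseline assessment already "will use all assessments irrespective of whether they fall in an analysis visit window".

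**Step 3. Can an eligible participant have a qualifying pre-dose value?**
- Bilirubin: exclusion 25 (Protocol 5.2) accepts an isolated value above 1.5xULN when direct bilirubin is below 35%. The note under exclusion 26 accepts Gilbert's syndrome. Such a participant meets the total-bilirubin row above 1.5xULN on the Baseline sample alone.
- AST: exclusions 24 and 25 name ALT and bilirubin. No criterion names AST.

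**Step 4. Do the footnotes prevent this?** The 28-day footnote requires bilirubin on or after the ALT elevation, so in that row a pre-dose bilirubin cannot be paired with a later ALT. The same-day footnote applies to ALT with ALP, and the direct-bilirubin rows have their own same-day condition. None of these requires a post-dose value, and none covers the other two combined rows.

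**Step 5. Illustration (all values assumed).**
- Baseline: bilirubin 1.6xULN; ALT, AST and ALP normal.
- On-therapy: bilirubin no higher than 1.4xULN; enzymes normal.
- TOC: bilirubin 1.4xULN; ALT 3.5xULN.

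Results for this participant:
- Third combined row, all visits: ALT 3.5 > 3 and bilirubin max(1.6, 1.4) = 1.6 > 1.5. Counted.
- Same row, post-baseline only: bilirubin 1.4 < 1.5. Not counted.
- Bilirubin change from Baseline to TOC: 1.4 − 1.6 = −0.2xULN, a fall.
- DMID bilirubin grade (SAP 6.2.4.1): 1.6xULN with normal enzymes lies in 1.5 to <2.0, Grade 2; 1.4xULN with raised ALT lies in 1.25 to <1.5, also Grade 2. There is no grade increase.
- DMID ALT grade: normal at Baseline, then 3.5xULN, which lies in 3.0 to 8.0, Grade 3. This is shown as a grade increase.
- Protocol 10.6: ALT of at least 3 but below 5xULN with bilirubin below 2xULN meets the increased-monitoring criteria if there are no symptoms and weekly monitoring is possible; otherwise a stopping criterion applies. Either way the participant is eligible for the liver monitoring/stopping summary.

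The enzyme rise is therefore visible elsewhere. What is misleading is the combined-row entry, because its bilirubin component was met only before treatment.

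**The case against.** The best defence is that the bracket is there to bring in unscheduled visits and never mentions Baseline. On that view Protocol 9.3.4 supplies the post-baseline scope, and since SAP 4.9 lists no change to laboratory scope, none was meant. That may well be the intention. But the Protocol sentence explains the treatment-policy strategy for discontinuation and is not a data rule for this table. If it does govern, the SAP bracket conflicts with it, and the list that opens "There were changes below to the originally planned statistical analysis specified in the protocol amendment 2" does not record the difference. Both readings lead to the same correction.

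A second defence is that the table may be displayed by visit, so that Baseline would stand apart. The 28-day footnote argues against this, because linking an ALT value to a later bilirubin makes sense only if the row pools visits.

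Third, the rows are titled abnormal results, not treatment-emergent ones, and the DMID grade-increase, change-from-baseline and liver monitoring/stopping summaries already separate much of what is new from what was present. This stands, and it is why the point is minor. These summaries do not reproduce the combined rows in their AST or 1.5xULN form: the combined bilirubin stopping criterion in Protocol 10.6 uses ALT of at least 3xULN with bilirubin of at least 2xULN and more than 35% direct.

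Fourth, pre-dose counts arise before dosing in a randomised, double-blind study, so they do not systematically favour either arm. This also stands.

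**Conclusion.** The point holds as one about wording with a limited descriptive effect. As written, the table can count allowed pre-dose bilirubin and pre-dose AST, and can mix pre-dose and post-dose components in two combined rows. Adding Baseline can only add cases, so it cannot hide a liver signal. No test and no primary conclusion is affected. The conclusion assumes that the bracket is programmed literally; the programming may already use post-baseline data, but the SAP does not say so.

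Three stronger readings are not supported:
- A reader might count affected rows and conclude that most of the table is compromised. The AST thresholds are nested and appear under both the AST and the ALT-or-AST headings, so a row count overstates the reach. Nothing is claimed here about the ALT-only rows.
- A reader might attach a percentage. The documents give no frequency of allowed high bilirubin or AST at Baseline, so any figure would be an unsupported assumption. The count may be zero.
- A reader might suppose that very high pre-dose bilirubin is freely admitted. Exclusion 25 sets no numerical ceiling on the isolated elevation, but exclusion 26 removes cirrhosis and unstable liver or biliary disease, including persistent jaundice, and Protocol 5.1 asks for otherwise healthy participants.

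**What to change.** In SAP 4.6.3.1, replace the bracket with: *any post-baseline assessment, planned or unscheduled*. State that both components of each combined row must be post-baseline. Show separately, by arm, how many participants already met each threshold at Baseline, in line with the vital-sign and ECG summaries. Extending the 28-day footnote to the other two combined rows is optional.

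The cost is one phrase, one sentence and one extra column. The data are already collected and no other analysis changes.
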